6.5. Prior and Concomitant Medication

Prior medications and concomitant medications will be coded using the WHO Drug Dictionary. The number and percentage of participants in the ITT population for each prior and concomitant medication will be summarized by WHO drug class and term. For the summary of concomitant medication, the medications will be included only if starting on or after the first dose of study treatment and no later than the last administration of retifanlimab, INCAGN02385, or INCAGN02390, whichever is later. Medications with missing start/end dates will be considered as concomitant medication in the summary. Post-treatment anticancer therapy will be summarized. Other medications will be provided in the listing. Drugs intended to manage irAEs, as well as prophylaxis/premedication used to prevent infusion reactions, may be summarized separately. Procedures and nondrug therapies will also be summarized/listed per eCRF.

7. EFFICACY

[Appendix A](#) provides a list of planned data displays. Sample data displays are included in a separate document.

7.1. General Considerations

All efficacy analyses will be performed using the ITT population. Efficacy endpoints of this study include PFS, objective response, DOR, disease control, based on RECIST v1.1, and OS. Response assessments, as determined by investigator, will be used for the efficacy analysis. Listings of response assessment at each visit will be provided. Unless otherwise stated, the strata identified in the randomization process will be used in all efficacy analyses.

7.2. Efficacy Hypotheses

Progression-Free Survival (Primary Endpoint):

- Hypothesis 1: TG3 is superior to TG1 with respect to PFS in all participants
- Hypothesis 2: TG2 is superior to TG1 with respect to PFS in all participants

7.3. Analysis of the Primary Efficacy Parameter

7.3.1. Response Assessment by RECIST

Overall disease status will be categorized using RECIST v1.1 ([Eisenhauer et al 2009](#)). Participants will have their overall response evaluated as CR, PR, SD, PD, or NE at each postbaseline radiologic assessment, which will be based on changes in target lesions, nontarget lesions, and appearance of new lesions.

7.3.2. Primary Efficacy Analysis

Progression-free survival is defined as the time from the date of randomization to the date of the first documented progression or death due to any cause, whichever occurs first. Progression-free survival will be based on investigator assessment per RECIST v1.1. Survival data will be analyzed by the Kaplan-Meier method, treating participants as censored if there is no observed death or radiologic disease progression before the cutoff date or the date that a new anticancer therapy is started. Censoring for PFS will follow the primary analysis algorithm outlined in [Table 6](#), which is based on regulatory guidelines ([FDA 2015](#)).

Table 6: Evaluation and Censoring of Progression-Free Survival

Situation	Primary Analysis	Sensitivity Analysis
No valid postbaseline response assessments in the absence of death prior to first scheduled tumor assessment	Censored at date of randomization	Censored at date of randomization
Progression documented between scheduled visits	Progressed at date of first overall response of PD	Progressed at date of first overall response of PD
Death before first PD assessment	Progressed at date of death	Progressed at date of death
No PD and no death; new anticancer treatment is not initiated	Censored at last disease assessment	Censored at last disease assessment if still on study therapy; progressed at treatment discontinuation otherwise
No PD prior to the new anticancer treatment which is initiated	Censored at last disease assessment before new anticancer treatment	Progressed at date of new anticancer treatment
No PD and no death after ≥ 2 missed consecutive disease assessments	Censored at last disease assessment prior to the ≥ 2 missed disease assessments	Censored at last disease assessment
PD or death documented after ≤ 1 missed disease assessment	Progressed at date of documented PD or death	Progressed at date of documented PD or death
PD or death documented after ≥ 2 missed consecutive disease assessments	Censored at last disease assessment prior to the ≥ 2 missed disease assessments	Progressed at date of documented PD or death

Note 1: Those participants who discontinued from the study or started a new anticancer treatment in the absence of documented progression will be considered as dropouts at the time of final analysis.

Note 2: The date on which any participant received high-dose palliative radiotherapy to sites of known disease that have been selected as target or nontarget lesions will be censored for PFS on the day the first fraction was delivered. Participants who receive a single fraction of radiotherapy to a single site of known bone metastasis will not be censored for PFS.

The nominal 1-sided p-value from the stratified log-rank test will be reported, stratified for LAG-3 expression status ($\geq 5\%$ vs $< 5\%$), PD-L1 CPS (1%-19% vs $\geq 20\%$), and HPV p16 status (p16-positive vs p16-negative). The strata identified in the randomization process will be used for the analysis.

The HR and its 95% CI will be estimated based on the stratified Cox regression model using the same stratification factors as for the log-rank test with Efron's method accounting for ties in event times (1977).

Kaplan-Meier curves for PFS will be presented by treatment groups. The Kaplan-Meier estimate of median PFS will be presented with its 95% CI. The 95% CI will be calculated using the generalization of Brookmeyer and Crowley's method (1982) with log-log transformation (Klein and Moeschberger 1997).

To evaluate the robustness of the PFS endpoint per RECIST v1.1 based on investigator review, a sensitivity analysis will handle participants who miss more than 1 disease assessment indifferently from participants who miss 0 or 1 disease assessment (ie, the status depends on if there is PD or death) and will handle participants who discontinue treatment or initiate an anticancer treatment after discontinuation of study treatment differently from the primary analysis. The censoring rules for the sensitivity analyses are also summarized in Table 6. Within each analysis, if a participant meets multiple criteria for censoring, the censoring criterion that occurs earliest will be applied.

The reverse Kaplan-Meier method will be used to estimate the median PFS follow-up time, presented with its 95% CI. The 95% CI will be calculated using the generalization of Brookmeyer and Crowley's method (1982) with log-log transformation (Klein and Moeschberger 1997).

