8.2.1.2. Tumor Imaging During the Study

The first imaging assessment should be performed 8 weeks (± 7 days) after the first dose of study treatment and then Q8W (± 7 days) for 12 months and then Q12W (± 7 days) thereafter until PD is determined. Imaging assessments may be done more frequently if clinically indicated. Imaging should not be delayed for delays in cycle starts.

Repeated brain imaging during the treatment phase will be performed only if the screening brain imaging was positive or as clinically indicated. If indicated, brain imaging should occur at same time (± 2 weeks) as disease assessment scans. Whenever feasible, contrast-enhanced brain MRI is preferred to CT.

Per RECIST v1.1, response should be confirmed by a repeat radiographic assessment not less than 4 weeks from the date that the response was first documented. The scan for confirmation of response may be performed at the earliest 4 weeks after the first indication of response or at the next scheduled scan, whichever is clinically indicated.

Imaging should continue to be performed until documented PD, the start of new anticancer treatment, withdrawal of consent, death, or the end of the study, whichever occurs first. A central imaging vendor will not be used in this study.

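### SAP Table 6 (and Protocol Table 20) both censors at randomization and counts as an event the same death: that of an unscanned participant who dies between the first and second scheduled scans

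*SAP*

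**What the plan says.** Rows are numbered here from the top of SAP Table 6 (Section 7.3.2). Protocol Table 20 (Section 10.4.1) lists its situations in the same order.

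- **Row 1**, "No valid postbaseline response assessments in the absence of death prior to first scheduled tumor assessment": censored at randomization in the primary and sensitivity columns of the SAP, and in all three columns of Protocol Table 20.
- **Row 3**, "Death before first PD assessment": event at the date of death, in every column.
- **Row 7**, "PD or death documented after ≤ 1 missed disease assessment": event at the documented date, in every column.
- **Row 8**, progression or death after two or more missed assessments: censored in the primary column, an event in the sensitivity columns.
- **Definition**: PFS runs from randomization "to the date of the first documented progression or death due to any cause, whichever occurs first".
- **Text on censoring**: "treating participants as censored if there is no observed death or radiologic disease progression before the cutoff date" or the start of new anticancer therapy.
- **Priority**: "if a participant meets multiple criteria for censoring, the censoring criterion that occurs earliest will be applied".
- **Scan timing** (Protocol Section 8.2.1.2): the first scan is due 8 weeks "after the first dose of study treatment and then Q8W", each within 7 days, for 12 months, then every 12 weeks.
- **Note 2 to Table 6**: a participant given high-dose palliative radiotherapy to a target or nontarget lesion "will be censored for PFS on the day the first fraction was delivered". Protocol Table 20 has no such rule, and SAP Section 10.1 does not list it as a change to the protocol-defined analyses.

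**The concern.** Row 1 spares from day-0 censoring only those who die before the first scheduled scan. Someone who misses that scan and dies before the second one is due has no valid assessment and did not die before week 8, so row 1 applies. Only one assessment was missed, so row 7 applies too, with the opposite result.

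Two programmers could each follow the table and build different primary datasets. If row 1 is applied, a death soon after week 8, one of the worst outcomes in the trial, contributes neither an event nor any time at risk, and the PFS estimate rises. A missed week-8 scan is foreseeable: Protocol Appendix C lets a CT be done at the next scheduled visit when pandemic conditions require it.

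**Working it through.** **1. The rows applied to one participant** (no week-8 scan, death at week 12, no new therapy)

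| Rule | Result |
|---|---|
| Row 1 | Censored, time 0 |
| Row 7 | Event at week 12 |
| Row 3 | Event at week 12, if the first PD assessment means the first one performed; not covered if it means the first one scheduled |
| PFS definition | Event at week 12 |
| Section text | Not censored, because a death was observed |

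The conflict with row 7 does not depend on interpretation; the conflict with row 3 does.

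**2. Does anything resolve it?** The priority sentence chooses among censoring criteria. This participant meets one censoring row and at least one event row, so the sentence is silent. The sensitivity column has the same entries in rows 1, 3 and 7. It also has a conflict of its own: for an unscanned participant who dies after two missed scans, row 1 censors at day 0 and row 8 counts an event. In the primary column rows 1 and 8 broadly agree for that participant.

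**3. The plan's power figure.** Inputs from SAP Section 3.2: 94 events per pair, HR 0.6, one-sided alpha 5%.

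Power = Φ(√d/2 × |ln HR| − z) = Φ(4.848 × 0.5108 − 1.645) = Φ(0.831) = 79.7%, against the stated 80.0%. At alpha 10% the result is 88.4%, as stated.

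**4. How many deaths are at stake.** The documents give no OS assumption for this trial and no rate of missed first scans, so both are assumed. Take exponential OS with a median of 10 months, the figure Protocol Section 2.1.2 gives for the platinum-based regimen. Week 8 is 1.840 months, week 16 is 3.680 months, and λ = ln 2/10 = 0.0693.

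- P(death in weeks 8 to 16) = exp(−0.1275) − exp(−0.2551) = 0.880 − 0.775 = 0.105.
- Per pair of 108: 108 × 0.1054 = 11.4 deaths.
- If 10% to 20% of these had no scan: 1.1 to 2.3 events.
- Varying median OS from 8 to 15 months and the unscanned share from 5% to 40%: 0.4 to 5.4 events.

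**5. Effect on power.** Losing 1, 2 or 5 of 94 events gives 79.3%, 79.0% or 77.8%.

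**6. Effect on the curve.** One arm was simulated with exponential PFS, median 3 months (Protocol Table 17) and 8-weekly scans. A stated share of participants dies unscanned in weeks 8 to 16.

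| Share | Week-16 PFS, deaths counted | Week-16 PFS, censored at day 0 |
|---|---|---|
| 2% | 41.7% | 42.5% |
| 5% | 40.6% | 42.7% |
| 10% | 38.5% | 42.8% |

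The share implied by step 4 at its middle values is 1% to 2%.

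**7. Note 2.** There are three cases after the first fraction.

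- No progression, no death and no later scan: row 4 gives the earlier date, and the priority sentence applies it. No unassessed time is credited.
- A later scan without progression: the participant is shown to be progression-free at the fraction date.
- Progression or death with no clean scan in between: the time from the last scan to the fraction is credited without an assessment. This is up to 8 weeks (1.84 months, 61% of the assumed 3-month median), or up to 12 weeks in the later schedule.

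In simulated pairs (54 per arm, medians 3 and 5 months, cutoff at month 20, radiotherapy assumed in 5% of TG1 and 10% of TG3), moving the censoring date back to the last scan changes the HR by under 0.01.

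**The case against.** The best defence is that a sensible reader would count the death. The definition includes death from any cause, the text censors only where no death was observed, and row 7 fits. On that view row 1 is loosely worded and nothing more. This is a fair reading and probably the intended one. But the same section says that censoring follows the table, and row 1 is an explicit entry in it, so the intention has to be guessed.

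It is also fair that little hangs on it numerically. SAP Section 10.2 removes Type I error control and describes the study as non-registrational, and the p-value is nominal.

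Three stronger readings are tempting, and the documents do not support them.

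- **That the priority sentence hands the case to row 1.** It ranks censoring criteria against each other, not censoring against events. The table gives two answers; it does not settle on losing the death.
- **That the rule favours a combination arm.** With unscanned deaths assumed in 2% of TG1 and 6% of TG3, the simulated HR moves from 0.62 to about 0.595. No rate or imbalance of this kind is in the documents. The shift is ln(0.62/0.595) = 0.041, about 0.2 of the standard error of log HR (2/√94 = 0.206).
- **That Note 2 credits every irradiated participant with unassessed time.** Only the third case in step 7 does so. Exposure is narrow: Protocol Section 6.6.2.1 says palliative radiation should not involve target lesions, Section 6.6.3 does not permit radiotherapy for tumor control, and Note 2 exempts a single fraction to a single bone metastasis. A larger HR contrast appears only if radiotherapy is counted as failure, which is a different question from the censoring date.

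**Conclusion.** The contradiction between row 1 and row 7 is real, stands in both documents, and is not resolved by the priority sentence or the sensitivity analysis. In the sensitivity column row 1 conflicts with row 8 as well.

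The expected size is small: about 1 to 2 events per pair and less than 1 point of power, with an upper end of about 5 events and 2 points. These figures rest on assumed OS and assumed missed-scan rates. If row 1 were applied, the bias in each arm's PFS curve would be upward; its direction between arms cannot be known from the documents. The reason to act is that the primary endpoint needs one definition that any programmer would reproduce.

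The Note 2 date is a minor inconsistency with a negligible effect on the HR. Because SAP Section 7.4.3 reuses the PFS censoring rules, it carries over to duration of response.

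**What to change.** **Row 1, primary analysis.** Limit it to participants with no valid postbaseline assessment and no death on or before the second scheduled assessment. State that limit as week 16 plus 7 days, counted from first dose, or from randomization if never dosed. Earlier deaths are events at the date of death, unless new anticancer therapy started first, in which case row 5 applies.

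**Row 1, sensitivity analysis.** Limit it to participants with no valid postbaseline assessment and no death at any time, so that it agrees with row 8.

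**Protocol Table 20.** Make the same change in its primary column and both sensitivity columns. Its row 5 is worded for participants without a death, so the exception for new therapy must be written out there.

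**Note 2.** Censor at the last disease assessment on or before the first fraction, say how radiotherapy is handled in the sensitivity column, and record the rule in SAP Section 10.1 as an addition to the Protocol.

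The cost is one row in each table and one note, with no new data and no change to sample size. It should be settled while the study team is still blinded.

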10.4. Statistical Analyses

10.4.1. Primary Analysis

Progression-free survival, defined as the time from the date of randomization to the date of the first documented progression or death due to any cause, whichever occurs first. Progression-free survival will be based on investigator assessment per RECIST v1.1. Survival data will be analyzed by the Kaplan-Meier method, treating participants with no observed death or disease progression as censored. Censoring for PFS will follow the primary analysis algorithm outlined in Table 20, which is based on regulatory guidelines (FDA 2015).

Table 20: Evaluation and Censoring of Progression-Free Survival

Situation	Primary Analysis	Sensitivity Analysis 1	Sensitivity Analysis 2
No valid postbaseline response assessments in the absence of death prior to first scheduled tumor assessment	Censored at date of randomization	Censored at date of randomization	Censored at date of randomization
Progression documented between scheduled visits	Progressed at date of first overall response of PD	Progressed at date of first overall response of PD	Progressed at date of first overall response of PD
Death before first PD assessment	Progressed at date of death	Progressed at date of death	Progressed at date of death
No PD and no death; new anticancer treatment is not initiated	Censored at last disease assessment	Censored at last disease assessment	Censored at last disease assessment if still on study therapy; progressed at treatment discontinuation otherwise
No PD and no death; new anticancer treatment is initiated	Censored at last disease assessment before new anticancer treatment	Censored at last disease assessment before new anticancer treatment	Progressed at date of new anticancer treatment
No PD and no death; after ≥ 2 missed disease assessments	Censored at last disease assessment prior to the ≥ 2 missed disease assessment	Censored at last disease assessment	Censored at last disease assessment

Table 20: Evaluation and Censoring of Progression-Free Survival (Continued)

Situation	Primary Analysis	Sensitivity Analysis 1	Sensitivity Analysis 2
PD or death documented after ≤ 1 missed disease assessment	Progressed at date of documented PD or death	Progressed at date of documented PD or death	Progressed at date of documented PD or death

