7.4. Analysis of the Secondary Efficacy Parameters

7.4.1. Best Overall Response and Objective Response Rate by RECIST

Best overall response for participants is the best response recorded postbaseline prior to and including the first PD, in the order of CR, PR, SD, PD, and NE determined by investigator assessment per RECIST v1.1.

The BOR will be determined from response assessments prior to or on the same day as new anticancer therapy. If any alternative cancer therapy is taken while on-study, then any subsequent assessments will be excluded from the BOR determination.

Best overall response for each participant is determined from the sequence of overall responses according to the following rules:

- CR = at least 2 consecutive determinations of CR at least 4 weeks apart before progression
- PR = at least 2 consecutive determinations of PR or better at least 4 weeks apart before progression (and not qualifying for a CR)
- SD = at least 1 SD assessment (or better) ≥ 6 months after start of treatment (and not qualifying for CR or PR)
- PD = meet progression criteria comparing with nadir (and not qualifying for CR, PR, or SD)
- NE = all other cases (ie, not qualifying for confirmed CR or PR and without SD after more than 7 weeks or PD)

In the case of SD, measurements must meet the SD criteria at least once after the date of first dose at a minimum interval of 6 months. Participants who fail to meet this criterion will have a

BOR of PD if the next available assessment after the initial assessment indicates PD, or a BOR of NE if there are no additional assessments available.

The largest percentage reduction in sum of diameters of target lesions will be listed. Spider plots (ie, percent change from baseline in sum of target lesions), waterfall plots (ie, best percentage change in sum of target lesions), and swimmer plots (ie, the overall response and duration of treatment) may be provided.

Objective response rate is defined as the proportion of participants with a CR or PR as BOR.

Estimates of ORR along with the exact 95% CIs using the Clopper-Pearson method will be computed for each treatment group.

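### SAP Table 6, read literally, censors a progression documented on the day new anticancer treatment starts; other SAP and Protocol wording counts that scan, so the same-day rule needs settling

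*SAP*

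**What the plan says.** **PFS.** The new-treatment row of SAP Table 6 (section 7.3.2) describes its situation as "No PD prior to the new anticancer treatment which is initiated". The primary analysis entry is "Censored at last disease assessment before new anticancer treatment" and the sensitivity entry is "Progressed at date of new anticancer treatment". The paragraph above the table sets this condition for censoring: "no observed death or radiologic disease progression before the cutoff date or the date that a new anticancer therapy is started". Note 1 below the table is worded differently: participants who "started a new anticancer treatment in the absence of documented progression will be considered as dropouts". Two other rows make documented PD an event on its date: one for PD between scheduled visits, one for PD after at most one missed assessment.

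**DOR.** SAP 7.4.3 applies the PFS censoring algorithm.

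**Best overall response (BOR).** SAP 7.4.1 states: "The BOR will be determined from response assessments prior to or on the same day as new anticancer therapy". PD is the best response only when CR, PR and SD of at least 6 months do not qualify.

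**Protocol.** The matching row of Table 20 (section 10.4.1) is headed "No PD and no death; new anticancer treatment is initiated".

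**The concern.** The SAP sets a same-day rule for response and none for the primary endpoint. If the Table 6 row is applied as worded, a PD found on the day the next therapy begins is not prior to that therapy, so an observed event becomes a censoring at the preceding scan. On the Q8W schedule that is about 8 weeks earlier.

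The observation discarded is an investigator-documented RECIST progression, which is what PFS measures. Censoring someone because progression and the switch share a date may be informative. The same scan would still feed BOR. Two programmers could reasonably code the tie differently, and the choice should not be made after unblinding.

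**Working it through.** **Step 1: the rules applied to one participant.** Suppose SD 56 days after randomization, then a first PD scan and the start of new therapy both on day 112.

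| Rule | Result |
|---|---|
| SAP Table 6 row and 7.3.2 text, primary PFS, read literally | Censored at day 56 |
| SAP Table 6 Note 1 and PD-event rows | Points to an event on day 112 |
| SAP Table 6, sensitivity analysis | Event on day 112 |
| Protocol Table 20, primary analysis | Event on day 112 (the new-treatment row requires no PD) |
| SAP 7.4.1, BOR | PD (same-day scan admitted; SD of at least 6 months not reached) |

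Two variants:

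- First PD at the first scan (day 56), with new therapy the same day. Only the baseline assessment precedes new therapy, so under the literal reading the participant is in effect censored at time zero. BOR is PD.
- Earlier confirmed PR, then PD on the day of new therapy. BOR stays PR. PFS and DOR are both censored under the literal reading.

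**Step 2: reproduce the plan's power.** Inputs from SAP 3.2 and Table 2: 94 events per pairwise comparison, HR 0.6, one-sided alpha 0.05, 1:1 within the pair. Schoenfeld's formula is power = Φ(|ln HR| × √d / 2 − z).

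- d = 94, z = 1.6449: 0.5108 × 9.695 / 2 − 1.6449 = 0.831, so power = 79.7% (SAP Table 2: 0.8000).
- d = 94, z = 1.2816 (alpha 0.10): 88.4% (SAP Table 2: 0.8840).
- HR at the bound, exp(−2 × 1.6449 / √94) = 0.712 (SAP Table 2: 0.7120).

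**Step 3: cost of lost events.** The documents do not say how often PD and new therapy share a date, so the number lost, k, is an assumption shown as a range. With a fixed data cutoff, HR 0.6 and one-sided alpha 0.05:

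| k lost | Events | Power |
|---|---|---|
| 0 | 94 | 79.7% |
| 1 | 93 | 79.3% |
| 2 | 92 | 79.0% |
| 3 | 91 | 78.6% |
| 5 | 89 | 77.8% |
| 10 | 84 | 75.7% |

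The loss per event is (79.7 − 75.7) / 10 = 0.4 points.

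**Step 4: when the loss is real.** SAP 3.2 triggers the final analysis at about 94 pairwise events or once the last participant has at least 8 months of follow-up, whichever is earlier. If the event count is the trigger, the analysis waits for 94 counted events and nominal power does not change. If follow-up is the trigger, censored events are not replaced.

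**The case against.** The best defence is that the SAP does not clearly censor this participant. Note 1 reserves dropout status for people without documented progression, and a same-day PD is documented. The PFS definition and the PD-event rows also cover the case. The tie-break in 7.3.2 ranks competing censoring criteria only; it does not set a censoring row above an event row. The word before may also be loose: the same sentence requires PD before the cutoff date, which taken strictly would censor a PD seen on the cutoff day. All of this stands as evidence of intent. It does not remove the conflict, because the row written for this situation says something else.

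The case is also likely to be uncommon. PFS takes the first PD date, and Protocol 6.5.5 plans a repeat scan at least 4 weeks later. Protocol 8.8.1 asks for the safety visit before new therapy that would start ahead of the 30-day visit. A PD that prompts a switch will usually be dated before it. Imaging at end of treatment, and until PD or new therapy, keeps a shared date possible.

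Power is not decisive here either. SAP 10.2 records that Type I error control was removed and that alpha served only the sample size calculation; the PFS p-value is nominal.

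Three stronger readings are tempting and not supported:

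- *The SAP certainly deletes these events.* Its own wording points both ways.
- *PFS and BOR always contradict each other for such a participant.* BOR is PD only if no earlier CR, PR or SD of at least 6 months qualifies.
- *Leaving a same-day scan without PD out of the PFS censoring date departs from the Protocol.* Table 20's primary analysis also uses the last assessment before new treatment. That point moves a censoring date and removes no event.

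**Conclusion.** A genuine but minor inconsistency. The explicit new-treatment row and the 7.3.2 sentence set a strictly-before cut that, taken literally, censors a documented same-day PD in primary PFS and in DOR. Note 1, the PD-event rows, Protocol Table 20 and the BOR window all lean towards using that scan. SAP 10.2 gives alignment with the Protocol as the aim of the Table 6 update, and on this tie the row does not achieve it.

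The sensitivity analysis limits the exposure because it places an event on the right date. It also changes the handling of treatment discontinuation and missed assessments, so it cannot isolate this rule.

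The power figure rests on three assumptions: HR 0.6, a number of same-day cases the documents do not supply, and an analysis that does not wait for 94 counted events. A reader might infer a material bias or power shortfall in the primary result; nothing in the documents supports a claim of that size.

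**What to change.** In the new-treatment row of SAP Table 6, word the situation as *No PD on or before the date new anticancer treatment is initiated*, and the primary analysis entry as *Censored at last disease assessment on or before the start of new anticancer treatment*. Change the matching sentence in 7.3.2 to on-or-before. DOR then follows through SAP 7.4.3, and all three endpoints use the cut already in 7.4.1. For a same-day scan without PD this shifts the censoring date relative to Protocol Table 20's wording, so record that in SAP 10.1.

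The cost is a few words in the SAP and the matching line of the programming specification, with no new data and no change to trial conduct. It should be settled before unblinding.
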